#### 2.3 Rationale

2.3.1 Rationale for combination of infigratinib with endocrine therapy: An analysis of 1,980 subjects with molecular data and 20 years of follow-up was recently performed. In this work, it was found that tumors classifying as integrative subtype 2 (characterized by the 11q13/14 amplification including FGF3/4/19 and accounting for approximately 5% of all HR+/HER2 breast tumors) or integrative subtype 6 (characterized by the 8p12 amplification including FGFR1 and account for approximately 5% of all HR+/HER2 tumors) exhibit an exceedingly high risk of distant relapse up to 20 years post-diagnosis (median 42 to 55%).  Substantial improvement in progression-free survival has been seen in HR+/HER2 metastatic breast cancer with the addition of CDK4/6 inhibition to endocrine therapy, 4-9 but virtually all tumors will eventually progress, leading to breast cancer-related death. The current treatment paradigm of metastatic HR+/HER2 FGF(R)-altered breast cancer does not include inhibition of the FGFR pathway. As a single agent in humans, infigratinib has shown some antitumor activity in pre-treated metastatic breast cancers with FGFR1 amplification, but not achieving the level of a partial response (Figure 1).  Breast tumors with FGF(R) pathway alterations are in urgent need of more effective therapies, and we propose that combining infigratinib with endocrine therapy could achieve this goal.

Accumulating preclinical and clinical data suggests that *FGFR1* amplification may drive endocrine therapy resistance in breast cancer.  For example, *FGFR1*-amplified cell lines showed resistance to 4-hydroxytamoxifen, which was reversed by RNA silencing of FGFR1.  ER+/*FGFR1*-amplified tumors treated with letrozole prior to surgery did not show decreases in proliferation as measured by Ki67 as is typically seen in sensitive tumors, and this primary resistance to aromatase inhibition appeared to be mediated by an upregulation of FGFR1 and FGF ligand expression allowing persistent activation of estrogen response.  Similarly, another study found that time to progression on first-line endocrine therapy was shorter in *FGFR1*-amplified ER+ metastatic breast cancers than in ER+ metastatic breast cancers that were not *FGFR1*-amplified, a difference not seen for first-line chemotherapy.  Combining lucitanib (a non-selective FGFR inhibitor) with fulvestrant improved growth inhibition of ER+/*FGFR1*-amplified cell lines and patient-derived xenografts.  Another study validated the finding of intrinsic endocrine therapy resistance in ER+/*FGFR1*-amplified primary tumors, and also reported a similar phenomenon for tumors with *CCND1/FGF3/4/19* amplification. 

In sum, these data provide a rationale for combining infigratinib with endocrine therapy may overcome the intrinsic endocrine therapy resistance of ER+/FGFR1-amplified or ER+/CCND1/FGF3/4/19-amplified tumors. For those subjects whose tumors have demonstrated primary or secondary resistance to endocrine therapy (ie, by progression on an aromatase inhibitor or fulvestrant), adding FGFR inhibition may allow these tumors to sensitize to endocrine therapy.

Notably, FGFR inhibition in combination with fulvestrant has been attempted previously in breast cancer, in a phase 2, randomized, placebo-controlled study of dovitinib in combination with fulvestrant in postmenopausal subjects with hormone receptor-positive, HER2-negative

breast cancer that progressed during or after prior endocrine therapy.  This study of N = 97 subjects showed median progression-free survival of 5.5 months in the dovitinib arm and 5.5 months in the placebo arm (HR 0.68) in the overall cohort. Findings were not significantly different in the FGF pathway-amplified subgroup (N = 31): median PFS 10.9 months in the dovitinib arm and 5.5 months in the placebo arm (HR 0.64). However, dovitinib is one of several non-selective multi-kinase inhibitors with greater impact on VEGFR than FGFR (another example is lucitinib), and subsequent studies have strongly suggested that these multi-kinase inhibitors may not effectively inhibit the FGFR pathway in subjects.  The efficacy of FGFR inhibition is most established thus far in FGFR-altered (most commonly FGFR3-mutated) advanced urothelial carcinoma, the setting for which the selective FGFR inhibitor erdafitinib received FDA approval as Balversa on 12 April 2019 (Accelerated Approval). Dovitinib was studied in this setting as well in a phase 2 study that treated N = 12 FGFR3-mutated and N = 31 FGFR3-wild-type advanced urothelial cancer subjects.  In this study, the ORR in the FGFR3-mutated subgroup was 0% (3.2% in the wild-type subgroup). Also, and importantly, no hyperphosphatemia was observed in these subjects, nor in other subjects who have been treated with dovitinib. Hyperphosphatemia is a key on-target effect of FGFR inhibition and its absence with dovitinib and other multi-kinase inhibitors suggests poor FGFR inhibition.  Conversely, in the phase 2 study of FGFR-altered advanced urothelial cancer that led to erdafitinib's approval, the ORR was 32% (28 of 87 subjects) with 69% experiencing hyperphosphatemia,  and in a similar phase 2 study of infigratinib, the ORR was 25% (16 of 67 subjects) with 50% experiencing hyperphosphatemia.  Dovitinib is no longer widely considered an effective FGFR inhibitor,  while the new generation of selective FGFR inhibitors are rapidly gaining ground in establishing their efficacy in FGFR-altered cancers.  We therefore believe it is time to assess the hypothesis that selective FGFR inhibition in combination with endocrine therapy may have a benefit for FGFR-altered hormone receptor-positive advanced breast cancer patients.

- 2.3.2 Comparison to other active trials: To our knowledge, there are 2 active clinical trials examining FGFR inhibition in combination with endocrine therapy in metastatic breast cancer, one of which also adds CDK4/6 inhibition. NCT04024436 opened October 2019 and is a nonrandomized phase 2 study will administer TAS-120 (Taiho) in combination with fulvestrant to 4 cohorts, 3 of which will have an FGFR2 amplification and 1 of which will have a high-level (ratio to centromere  $\geq 5$ ) FGFR1 amplification. Neither of these studies will examine the efficacy of FGFR inhibition in combination with endocrine therapy in tumors harboring amplification of the ligand (FGF3; integrative subtype 2). The hypothesis driving the present trial is that the unique drivers identified via integrative subtyping (a subset of tumors with FGFR1 amplification classifying as integrative subtype 6; and a subset of tumors with FGF3 amplification classifying as integrative subtype 2) will be uniquely sensitive to FGFR inhibition.
- 2.3.3 Rationale for dose of tamoxifen: The dose and schedule selected for tamoxifen (20 mg/day by mouth continuously) is FDA-approved for the treatment of ER+ metastatic breast cancer.

#### 2.4 Screening Tumor Sequencing Assays

Potential subjects will be eligible if their tumor classifies as integrative cluster 2 (IC2) or 6 (IC6) based on the results of the FoundationOne (F1CDx) FDA-approved assay. There are 11 validated integrative subtypes or clusters of breast cancer, defined initially from the METABRIC cohort based on the integration of genomic copy number alterations and transcriptional profiles.  Our recent study examining 20 years of clinical follow-up from 1,980 subjects in the initial METABRIC cohort revealed substantial variability in the risk of relapse amongst HR+/HER2 subjects.  In particular, integrative subtypes 1, 2, 6, and 9 exhibited exceedingly high (median 42 to 55%) risk of distant relapse up to 20 years post-diagnosis. Each of these integrative subtypes is characterized by distinct copy number amplification events and concomitant over-expression of candidate driver genes: integrative subtype 2 has the FGF3/FGF4/FGF19, CCND1 (11q13/14) amplification and integrative subtype 6 has the FGFR1 (8p12) amplification. While these characteristic amplifications are almost universally present within tumors classifying as the relevant integrative subtype, the converse is not true: only approximately one-quarter of ER+/HER2 tumors that carry the CCND1/FGF3/4/19 amplification classify as integrative subtype 2, and approximately one-half of ER+/HER2 tumors that carry the *FGFR1* amplification classify as integrative subtype 6. It is plausible that these amplifications may be passenger events rather than driver events in the tumors that do not classify as the relevant integrative subtypes. Using additional information from targeted sequencing panels can improve the accuracy of integrative cluster classification, and we hypothesize better delineate in which tumors the FGFR pathway is the oncogenic driver than the simple presence of the amplification.  Thus, subjects will be eligible if their tumor's F1CDx results are consistent with integrative cluster 2 or 6, per the classifier. The classifier was developed to predict integrative cluster classification from the copy number values and mutational status of the genes on the F1CDx panel in two large cohorts of breast tumors. METABRIC  and The Cancer Genome Atlas . This classifier will be applied to the integer copy number values and gene mutation calls generated by the F1CDx assay and analysis.

# 2.5 Study Design

- The primary purpose for this study is treatment. The protocol is designed to evaluate one or more interventions for treating a disease, syndrome, or condition.
- The interventional model is Sequential.
- The number of intervention arms is up to 3.
- The study will be not be masked (not blinded).
- The study will be not be randomized.

This is a phase 1b study evaluating the safety and tolerability of infigratinib. Cohort 1 will utilize the combination of tamoxifen and infigratinib. We anticipate that this combination may play a role in the future development of infigratinib for hormone receptor-positive breast cancer, necessitating the establishment of their safety. For example, tamoxifen and infigratinib might be used in the early-stage, (neo)adjuvant setting as well as the late-stage, metastatic setting.

In Cohort 1, up to 3 dose levels of infigratinib may be evaluated (125 mg; 100 mg; and 75 mg) in combination with tamoxifen. This pilot study is a necessary step for the future development of infigratinib in combination with tamoxifen and will serve as a safety run-in evaluation for a follow-up study. For this cohort, a 3 + 3 design will be employed starting at 100 mg, and allowing subjects who start at 100 mg to escalate to 125 mg (see Section 12.4).

#### 2.6 Correlative Studies Background

- 2.6.1 Organoid cultures: Three-dimensional organoid cultures established from viable tumor cells have the potential to re-capitulate in vitro subject- and tumor-specific phenotypes, enabling the study of drug response and tumor evolution in the lab. 32-34 Tumor organoid cultures can be established as a renewable source of tissue for *in vitro* and *in vivo* experimentation; they are amenable to high-throughput drug screens and complementing xenograft-based approaches. Organoid culture can be used to evaluate the efficacy of novel therapeutic agents in specific genetic contexts. It is planned to establish organoids from tumors in this study, classifying as integrative subtypes 2 and 6, allowing testing of novel drug combinations to improve response and overcome resistance to FGFR inhibition in these high-risk subgroups. Furthermore, as these organoids will be treated in vitro with the same agents that the study subjects from whose tumors they were derived will be, we will be able to compare response between the in vitro and subjects. We will also be able to compare the genomic alterations that arise with treatment in subjects (Section 2.6.2) with those that arise with treatment in the organoids. These experiments may inform our understanding of genomic determinants of sensitivity and resistance to FGFR inhibition, as well as the optimal combinations of therapies to produce response in FGFR-altered breast tumors.
- 2.6.2 Cell-free DNA analyses: Cell-free DNA is believed to be representative of the heterogeneity present even in micro-metastatic lesions.  Thus, it may better capture the spectrum of subclonal populations with the potential to grow in response to therapy than serial tumor biopsies. Furthermore, it has been shown that cell-free DNA sequencing can detect and characterize clonal dynamics in metastatic breast cancer.  It is planned to collect blood from subjects prior to initiation of study drug, after the first 2 weeks of therapy, and at time of confirmed progression. The blood samples will be separated into plasma and buffy coat and banked. Sequencing (eg, whole-exome or whole-genome) of the cell-free DNA extracted from these banked plasma samples will allow us to identify novel mutations or copy number changes that appear at time of progression in subjects who initially responded, as well as to compare baseline genomic changes between responders and non-responders. The banked buffy coat samples will allow us to identify somatic variants that act as driver mutations and compare them to a matched normal sample through tumor-normal whole-genome sequencing. Furthermore, we can cross-reference these findings with genomic findings in the organoid models (Section 2.6.1). These analyses may allow us to identify genetic mechanisms of resistance to the study drug and/or endocrine therapy.
- 2.6.3 Proteomic profiling: Proteomic changes may be examined in tumor cells and the surrounding microenvironment *in situ* to delineate compensatory signaling pathways and mechanisms of response/resistance to the evaluated targeted agents. Paired pre- and

post-treatment tissue samples from the trial may be profiled on the Nanostring GEOMx Digital Spatial Profiling (DSP) platform (Research Use Only)  or with mutiplexed ion beam imaging (MIBI).  There is growing evidence that functional heterogeneity in the tumor and microenvironment contribute to treatment response, highlighting the importance of spatially resolved approaches such as DSP. DSP enables geographic and phenotypic selection of tissue regions – for example, those that are enriched for pancytokeratin-positive tumor cells. Molecular changes observed with treatment may inform intelligent combinations of therapy in the future to overcome primary resistance or enhance treatment response.

#### 3. PARTICIPANT SELECTION AND ENROLLMENT PROCEDURES

Inclusion and Exclusion Criteria are provided on Participant Eligibility Checklist following. This document may be extracted from this document for use in screening potential subjects.

The Participant Eligibility Checklist in the following subsection must be completed in its entirety for each subject prior to registration. The Participant Eligibility Checklist may be extracted from this document for use in screening potential subjects. The completed, signed, and dated checklist must be retained in the subject's study file, and the study's Regulatory Binder. Screening results will be collectively documented on the Study Participant Log.

Pursuant to Stanford Medicine SOP "Confirmation of Participant Eligibility in Clinical Trials," the treating Physician (investigator); the Study Coordinator; and a third reviewer from the study team (eg, investigator or back-up study coordinator) will verify that the subject's eligibility is accurate; complete; and legible in source records. A description of the eligibility verification process should be included in the EPIC or other Electronic Medical Record progress note.

# **Participant Eligibility Checklist**

#### I. Protocol Information

Protocol Title:	A Phase 1B Study of Infigratinib in Combination with Tamoxifen in Hormone Receptor-Positive, HER2-Negative, FGFR-Altered Advanced Breast Cancer		
eProtocol number: OnCore number:	IRB-53650 BRS0113		
Principal Investigator [per 21CFR§312.3(b)]:	[name]		
II Subject Information			

#### II. Subject Information

Subject name / Unique ID:		/
Gender	☐ Male	☐ Female

# 3.1 Inclusion Criteria

	Prospective Participant Must MATCH ALL these Inclusion Criteria to be Eligible	Yes	No	Supporting Documentation *
1.	History of biopsy-proven ER-positive and/or PR-positive, HER2-negative breast cancer and radiographic evidence of metastatic disease, or locally recurrent unresectable disease. ER-positivity and PR-positivity are defined as ≥ 1% cells staining positive by immunohistochemistry. HER2-negativity is defined by IHC or FISH, per ASCO-CAP 2018 guidelines			
2.	Cancer subtype indicative of alterations to the fibroblast growth factor ligand or receptor (FGF/FGFR alteration): Predicted integrative (IntClust) subtype classification of IC2 or IC6 according classifier on targeted sequencing data from FoundationOne.			

IRB-53650 Version 11 Page 24 of 72 11 November 2021

	Prospective Participant Must MATCH ALL these Inclusion Criteria to be Eligible	Yes	No	Supporting Documentation *
3.	Evaluable or measurable disease.  Cohort 1 only: Evaluable or measurable disease, as defined by RECIST v1.1. Bone-only disease is acceptable.			
4.	≥ 18 years old			
5.	Eastern Cooperative Oncology Group (ECOG) performance status 0 to 2			
6.	Prior cancer therapy (except for endocrine therapy, denosumab, or bisphosphonates) must be discontinued for 2 weeks prior to initiation of study drugs. Recovery from adverse events of previous cancer therapies to baseline or Grade 1 except for alopecia or stable Grade 2 neuropathy. Radiotherapy must also be completed at least 2 weeks prior to initiation of study drugs			
7.	Absolute neutrophil count (ANC) ≥ 1,000/mm 			
8.	Platelets ≥ 75,000/mm 			
9.	Hemoglobin ≥ 9.0 g/dL			
10.	Total bilirubin ≤ 1.8 mg/dL (unless documented Gilbert's disease)			
11.	Aspartate aminotransferase (AST) and alanine aminotransferase (ALT) < 90 U/L			
12.	Estimated glomerular filtration rate (GFR) ≥ 45 mL/min			
13.	Phosphorus between 2.5 and 4.5 mg/dL, inclusive			
14.	Total corrected (for albumin) serum calcium between 8.5 and 10.5 mg/dL, inclusive			
15.	Amylase < 200 U/L			
16.	Lipase < 120 U/L			
17.	Ability to understand and the willingness to sign a written informed consent document			

Prospective Participant Must MATCH ALL these Inclusion Criteria to be Eligible	Yes	No	Supporting Documentation *
18. Agrees to take sevelamer, if indicated, and has no contraindications to use of this medication (that is: known hypersensitivity to sevelamer or component of the formulation; bowel obstruction; active bowel mucosal injury such as ulcerative colitis or gastrointestinal bleeding).			
19. Agrees to follow low-phosphate diet, if indicated			
20. Able to swallow and retain oral medication			

 
21. Women must be postmenopausal, defined as (at least one of):
 
≥ 60 years of age;
 
• amenorrhea for at least 24 months;
 
• amenorrhea for at least 12 months with serum estradiol < 20 pg/mL;
 
• prior bilateral oophorectomy;
 
OR
 
• treatment with a luteinizing hormone (LH)-releasing hormone agonist (such as goserelin acetate or leuprolide acetate) initiated at least 28 days prior to study enrollment.
 
			
22. Women being treated with a LH-releasing agonist but who are otherwise of childbearing potential (did not undergo total hysterectomy or bilateral tubal ligation at least 6 weeks before first dose of study drug) must have a negative pregnancy test within 7 days of the first dose of study drug.			
23. Women who are being treated with an LH-releasing agonist but are otherwise of childbearing potential must agree to use barrier contraception or an intrauterine device while taking study drug and for 3 months following their last dose of study drug. Alternatively, total abstinence is acceptable if preferred by the subject.			

Prospective Participant Must MATCH ALL these Inclusion Criteria to be Eligible	Yes	No	Supporting Documentation *
24. Sexually-active men must agree to use a condom during intercourse while taking drug and for 3 months after the last dose of the study drug and should not father a child during this period.  A condom is required to be used also by vasectomized men as well as during intercourse with a male partner to prevent delivery of the drug via seminal fluid.			

# 3.2 Exclusion Criteria

	Prospective Participants Must NOT Match ANY of These Exclusion Criteria	Yes	No	Supporting Documentation *
1.	History of another primary malignancy within 3 years except adequately treated in situ carcinoma of the cervix or non-melanoma carcinoma of the skin or any other curatively treated malignancy that is not expected to require treatment for recurrence during the course of the study.			
2.	Neurologic symptoms related to central nervous system metastases requiring increasing doses of corticosteroids. Note that subjects with central nervous system metastases ARE eligible if they are on a stable corticosteroid dose for at least 2 weeks preceding study entry.			
3.	Current evidence of corneal or retinal disorder/keratopathy including, but not limited to, bullous/band keratopathy, corneal abrasion, inflammation/ulceration, keratoconjunctivitis, confirmed by ophthalmologic examination. Subjects with asymptomatic ophthalmologic conditions assessed by the investigator to pose minimal risk for study participation may be enrolled in the study.			

	Prospective Participants Must NOT Match ANY of These Exclusion Criteria	Yes	No	Supporting Documentation *
4.	Current evidence of extensive tissue calcification including, but not limited to, the soft tissue, kidneys, intestine, myocardium, and lung with the exception of calcified lymph nodes, minor pulmonary parenchymal calcifications, and asymptomatic coronary calcification.			
5.	Impairment of gastrointestinal (GI) function or GI disease that may significantly alter the absorption of oral infigratinib (eg, ulcerative diseases, uncontrolled nausea, vomiting, diarrhea, malabsorption syndrome, small bowel resection).			
6.	Current evidence of endocrine alterations of calcium/phosphate homeostasis, eg, parathyroid disorders, history of parathyroidectomy, tumor lysis, or tumoral calcinosis.			
7.	Currently receiving or planning during study participation to receive treatment with agents that are known strong inducers or inhibitors of CYP3A4 and medications which increase serum phosphorus and/or calcium concentration. Subjects are not permitted to receive enzyme-inducing anti-epileptic drugs, including carbamazepine, phenytoin, phenobarbital, and primidone. See Appendix A for a list of prohibited concomitant medications and supplements.			
8.	Has consumed grapefruit, grapefruit juice, grapefruit hybrids, pomegranates, star fruits, pomelos, Seville oranges, or products containing juice of these fruits within 7 days prior to first dose of study drug.			
9.	Have used amiodarone within 90 days prior to first dose of study drug.			
10.	Has used medications known to prolong the QT interval and/or are associated with a risk of Torsades de Pointes (TdP) 7 days prior to first dose of study drug. See Appendix A for a list of prohibited concomitant medications and supplements.			

Prospective Participants Must NOT Match ANY of These Exclusion Criteria	Yes	No	Supporting Documentation *
11. Has used calcium or vitamin D within 3 days prior to first dose of study drug. Calcium supplementation may subsequently be used as clinically indicated (for hypocalcemia) on study.			
12. Have clinically significant cardiac disease including any of the following:			

 
a. Congestive heart failure requiring treatment (New York Heart Association Grade ≥ 2), left ventricular ejection fraction (LVEF) < 50% or local lower limit of normal as determined by multiple gated acquisition (MUGA) scan or echocardiogram (ECHO), or uncontrolled hypertension (refer to the European Society of Cardiology and European Society of Hypertension guidelines [Williams et al., 2018])
 
b. Presence of Common Terminology Criteria for Adverse Events (CTCAE) v5.0 Grade ≥ 2 ventricular arrhythmias, atrial fibrillation, bradycardia, or conduction abnormality
 
c. Unstable angina pectoris or acute myocardial infarction ≤ 3 months prior to first dose of study drug
 
d. Corrected QT interval-Fredericia (QTcF) > 470 msec (males and females). Note: If the QTcF is > 470 msec in the first electrocardiogram (ECG), a total of 3 ECGs separated by at least 5 minutes should be performed. If the average of these 3 consecutive results for QTcF is ≤ 470 msec, the subject meets eligibility in this regard.
 
e. Known history of congenital long QT syndrome
 
			
13. Have had a recent (≤ 3 months) transient ischemic			
attack or stroke.			
14. Pregnant or nursing			

\* All subject files must include supporting documentation to confirm subject eligibility. The method of confirmation can include, but is not limited to, laboratory test results, radiology test results, subject self-report, and medical record review.

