# 4.1 General Concomitant Medication and Supportive Care Guidelines

#### 4.1.1 Concomitant Medication

Administration of other anticancer therapies within 2 weeks of enrollment, except ongoing administration of a bisphosphonate drug or denosumab as treatment for bone metastasis or ongoing administration of a luteinizing hormone-releasing hormone agonist (such as goserelin acetate or leuprolide acetate) or other endocrine therapy, is prohibited.

Palliative radiotherapy on study is permitted for the treatment of painful bony lesions providing the lesions were known at the time of study entry and the investigator clearly indicates that the need for palliative radiotherapy is not indicative of disease progression. In view of the current lack of data about the interaction of infigratinib with radiotherapy, infigratinib treatment should be interrupted during palliative radiotherapy, resuming infigratinib treatment after recovery to ≤ Grade 1 radiotherapy-related toxicity.

Details for specific medications prohibited while on study are provided in Appendix A. The rationale for the restricted medications is provided below.

Strong inhibitors of CYP3A4 such as the ones listed in Appendix A are prohibited because infigratinib is a likely substrate of this isoenzyme.

Strong inducers of CYP3A4 are prohibited because their usage may decrease the exposure of infigratinib. Therefore, agents such as those listed in Appendix A are prohibited. Please note that the list may not be exhaustive.

Subjects must also avoid the consumption of grapefruits; grapefruit juice; grapefruit hybrids; pomegranates; star fruits; pomelos; Seville oranges; or juice within 7 days prior to the first dose of infigratinib and throughout the treatment period due to a potential CYP3A4 interaction with study drug.

Medications that increase the serum levels of phosphorus and/or calcium are prohibited.

Preliminary clinical data have shown that infigratinib has no effect on cardiac conduction or ECG intervals (See current version of the infigratinib Investigator's Brochure). However, medications that are known to prolong the QT/QTc interval or induce TdP (risk of TdP/QT prolongation) are prohibited. List of these medications is given in Appendix A. Please note that the list might not be comprehensive.

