Other Clinical Assessment	t		•					•		
Adverse event assessment 	Х			Monitor	and record at every study visit			х	Х	Х
Concomitant medications 	Х	Monitor			and reco	d at every	/ study visit	Х	Х	

- 1. Informed Consent: Must be obtained prior to undergoing any study specific procedure and may occur prior to the 21-day screening period. Registration will considered to be signed informed consent with triple-signed eligibility checklist, with the final signature being the Stanford Principal Investigator or his/her designee.
- 2. Medical History / Tumor History: To be collected within 21 days prior to C1D1. Includes history of other diseases (active or resolved) and concomitant illnesses. Oncology history includes information on prior regimens (including dosing and duration of administration, description of best response observed, recurrence date), surgery and radiation therapy. It also includes review of the predicted integrative subtype from FoundationOne. These assays may also be done during screening, as indicated (see footnote 22, "Tumor sequencing").
- **3. Physical Examination:** Includes an examination of major body systems. Weight for the purposes of dose calculation will be recorded at screening and within 7 days pre-dose Day 1 of each cycle. Weight will also be collected at End of Treatment. Height will be measured at baseline.

A Phase 1B Study of Infigratinib in Combination with Tamoxifen in

Hormone Receptor-positive, HER2-negative, FGFR-altered Advanced Breast Cancer

4. ECOG Performance Status:

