### **APPENDICES**

# APPENDIX A: List of prohibited medications and substances

Category	Drug Names	
Strong inhibitors of CYP3A4	clarithromycin, conivaptan, fluconazole, fluvoxamine, indinavir, itraconazole, ketoconazole, lopinavir, mibefradil, miconazole, nefazodone, nelfinavir, norfloxacin, posaconazole, ritonavir, saquinavir, telithromycin, voriconazole	
	grapefruit, grapefruit juice, grapefruit hybrids, pomegranates, star fruits, pomelos, Seville oranges or products containing juice of these fruits	
Strong inducers of CYP3A4	avasimibe, carbamazepine, nevirapine, phenobarbital, phenytoin, pioglitazone, primidone, rifabutin, rifampin, St. John's wort, troglitazone	
Medications which increase serum phosphorus and/or calcium	calcium, parathyroid hormone, phosphate, vitamin D (including multivitamins containing vitamin D)	
Medications with established potential for QT prolongation or TdP	amiodarone, anagrelide, arsenic trioxide, astemizole (off US market), azithromycin, bepridil (off US market), chloroquine, chlorpromazine, cisapride (off US market), citalopram, clarithromycin, cocaine, disopyramide, dofetilide, domperidone (not on US market), dronedarone, droperidol, erythromycin, escitalopram, flecainide, halofantrine, haloperidol, ibutilide, levofloxacin, levomethadyl (off US market), mesoridazine (off US market), methadone, moxifloxacin, pentamidine, pimozide, probucol (off US market), procainamide (oral off US market), quinidine, sevoflurane, sotalol, sparfloxacin (off US market), sulpiride (not on US market), terfenadine (off US market), thioridazine, vandetanib	

Abbreviations: CYP – cytochrome P; TdP – Torsades de Pointes; US – United States.

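### Strong CYP3A4 inhibitors and inducers are barred only if current or planned, with no interval before first dose, although grapefruit-type foods in the same Appendix A row must stop 7 days before.

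*Combined protocol and SAP*

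**What the plan says.** Exclusion 7 (Section 3.2) covers a subject who is "Currently receiving or planning during study participation to receive treatment with agents that are known strong inducers or inhibitors of CYP3A4" and refers to Appendix A for the list. It also disallows enzyme-inducing anti-epileptics, without a time frame. Section 4.1.1 prohibits strong inhibitors because infigratinib is a likely CYP3A4 substrate. On inducers it states: "Strong inducers of CYP3A4 are prohibited because their usage may decrease the exposure of infigratinib". It gives no interval before first dose for either class, and Section 2.2.6, Section 5.1.2, the Study Calendar footnotes and Appendix A add none.

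Other prohibited items do have an interval:

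- Exclusion 8 covers grapefruit-type fruit, juice and "products containing juice of these fruits within 7 days prior to first dose of study drug". Section 4.1.1 repeats the limit: "within 7 days prior to the first dose of infigratinib and throughout the treatment period due to a potential CYP3A4 interaction with study drug". In Appendix A these foods ("grapefruit, grapefruit juice, grapefruit hybrids, pomegranates, star fruits, pomelos, Seville oranges or products containing juice of these fruits") are in the row for strong CYP3A4 inhibitors.
- Exclusion 9 sets 90 days for amiodarone.
- Exclusion 10 covers use of "medications known to prolong the QT interval and/or are associated with a risk of Torsades de Pointes (TdP) 7 days prior to first dose".
- Exclusion 11 reads: "Has used calcium or vitamin D within 3 days prior to first dose of study drug".

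On timing, footnote 1 of the Study Calendar states: "Registration will considered to be signed informed consent with triple-signed eligibility checklist". The calendar places registration no more than 7 days before Cycle 1 Day 1.

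**The concern.** Read literally, the rule excludes someone who drank grapefruit juice five days before first dose but admits someone who took ketoconazole or rifampin until the day before sign-off. A subject still on the drug at sign-off fails. One who has just stopped passes and can start Cycle 1 at once.

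Section 2.2.6 expects CYP3A inhibitors and inducers to matter clinically, because infigratinib probably undergoes substantial intestinal first-pass metabolism by this route. If the effect persists after the drug is stopped, exposure early in Cycle 1 does not correspond to the assigned dose. Residual inhibition could produce a DLT that is charged to the nominal dose. Residual induction could help a subject through the window and support a dose that was not fully tested. Section 12.4 can declare a dose safe on 0 DLTs in 3 subjects, so each subject weighs heavily. The Study Calendar has no routine infigratinib sampling, and Table 6 asks for a drug level only after marked QTcF prolongation or serious arrhythmia, so altered exposure would usually go unmeasured.

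**Working it through.** **Coverage of the listed drugs (Appendix A, by name)**

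- Strong inhibitors: 18 drugs. Clarithromycin is also in the QT row, so Exclusion 10 gives it 7 days. That leaves 17.
- Strong inducers: 11 drugs, none in the QT row. That leaves 11.
- Without an explicit interval: 17 + 11 = 28 of 29.

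Exclusion 10 is worded by property, so it could reach another listed drug. The count is of names, not of subjects at risk.

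**Illustrative effect on the 3+3 decision at 100 mg**

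The plan gives no figure to reproduce, and the documents give no frequency of recent use, no offset time and no effect size. Inputs:

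- Baseline DLT risk p = 1/6, from 1 DLT in 6 subjects at 100 mg as a single agent (Section 2.2.9).
- Full-window risk r for an affected subject: 1/3 if inhibited, 0.10 or 0.05 if induced (assumed).
- Carry-over d = 7 or 14 days (assumed).
- Window W = 56 calendar days (two 28-day cycles) or 42 planned dosing days (two 21-day blocks).
- Constant hazard, and exactly one of the first three subjects affected (assumed).

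Risk for the affected subject:

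q = 1 − (1 − r)^(d/W) × (1 − p)^((W − d)/W)

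Under Section 12.4, 100 mg passes with 0 DLTs in 3 or 1 in 6:

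Pass = (1 − p)²(1 − q) + [(1 − p)²q + 2p(1 − p)(1 − q)] × (1 − p)³

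Baseline, q = 1/6: 0.5787 + 0.3472 × 0.5787 = 0.780.

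Example with r = 1/3, W = 42, d = 7: q = 0.197, and Pass = 0.5576 + 0.3599 × 0.5787 = 0.766.

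| r | W | Pass, d = 7 | Pass, d = 14 | Pass, d = W |
|---|---|---|---|---|
| 1/3 | 56 | 0.769 | 0.759 | 0.704 |
| 1/3 | 42 | 0.766 | 0.753 | 0.704 |
| 0.10 | 56 | 0.783 | 0.787 | 0.810 |
| 0.10 | 42 | 0.785 | 0.789 | 0.810 |
| 0.05 | 56 | 0.786 | 0.792 | 0.833 |
| 0.05 | 42 | 0.788 | 0.797 | 0.833 |

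Against 0.780, the shift is about 0.4 to 1.4 percentage points for 7 days of carry-over and 0.7 to 2.7 points for 14 days. The last column is a bound for carry-over lasting the whole window; nothing in the documents suggests that duration.

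**The case against.** The strongest reply is that the effect is too small to matter, and that the model may overstate it. The shifts apply only if an affected subject is among the first three, and that frequency is unknown. Section 2.2.9 gives a median of 22 days to interruption for hyperphosphatemia under continuous dosing, and Section 2.2.3 reports accumulation ratios of 3 to 8 by Days 15 and 28. Many Table 7 criteria need more than 7 days of persistence or 14 days of phosphate-lowering therapy. An effect confined to the first week is poorly placed to trigger those DLTs, although criteria such as phosphorus above 10.0 mg/dL or QTcF above 500 ms act immediately. A subject who escalates to 125 mg does so from Cycle 3, when carry-over of 7 or 14 days has ended. All of this stands, and it limits the statistical weight of the point.

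The consistency argument also has limits. Phosphate and parathyroid hormone share an Appendix A row with calcium and vitamin D and have no interval either, and a look-back is natural wording for a food eaten now and then. But the grapefruit interval is justified by the same CYP3A4 interaction, and calcium and vitamin D get a look-back in Exclusion 11 although Exclusion 7 already bars current use of drugs that raise calcium. The plan therefore does not rely on a ban on current use to cover recent use.

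The existing safeguards are real: review by three people, medication recording from 30 days before treatment (footnote 22), chemistry and phosphorus on C1D4 and C1D15, the Table 6 hold and reduction rules, and a 100 mg start below the single-agent maximum tolerated dose of 125 mg. They make recent use visible and manage toxicity. They do not bar the subject, detect under-exposure or correct the dose attribution.

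The documents cannot show that 7 days is long enough for every listed drug. The Investigator's Brochure and Pharmacy Manual, not available here, may carry washout guidance, but the eligibility checklist as written does not apply any.

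**Conclusion.** The concern holds. Followed exactly, the eligibility rule admits a subject who has just stopped a strong CYP3A4 inhibitor or inducer into the DLT window, while a weaker case for concern, recent grapefruit, is excluded. Confidence is high for the omission, which is a matter of text. The numerical effect is illustrative only: it rests on an assumed constant hazard, assumed risk shifts and exactly one affected subject among the first three, and on those terms it is small. The reasons to act are subject safety, clean attribution of DLTs to dose and internal consistency. This is an inexpensive improvement, not a flaw that threatens the trial's conclusion.

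**What to change.** Amend Exclusion 7 so that the Appendix A strong CYP3A4 inhibitors and inducers are excluded if used currently or within 7 days before the first dose of study drug, matching Exclusion 8. Repeat the interval in Section 4.1.1. Set a longer interval for inducers if clinical pharmacology advises it. In the DLT listing, flag any use of these drugs in the 30 days before treatment; footnote 22 already requires that record.

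The cost is one line in each section and a short start delay for affected subjects, which should usually fit within the 21-day screening period. Moderate CYP3A4 agents (18 inhibitors and 12 inducers in Appendix B) would still be allowed with caution, so the change removes carry-over from strong agents but not all CYP3A4-related variation.
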